1.2 Study flow chart

1.3 Study schedule

Project name	Screening/Baseline Period	Treatment period					EOT visit	Efficacy follow-up	Survival follow-up
	-w3-w0	D1	D8	D1 5	D2 2	D2 9	D29	D29 to PD Date	PD date to death
Informed consent	✓								
Check Inclusion and exclusion criteria	✓								
Baseline and demographic data	✓								
Vital signs and physical examination	◆	✓	✓	✓	✓	✓	✓		
ECOG PS	◆	✓	✓	✓	✓	✓	✓		
Quality of life ⁶	◆	✓	✓	✓	✓	✓	✓	✓	✓
Charlson Comorbidity Index	✓								
Nutritional status	✓								
Blood routine examination	◆	✓	✓	✓	✓	✓	✓	■	
Urinalysis	◆	✓	✓	✓	✓	✓	✓	■	
Bowel routine	◆	✓	✓	✓	✓	✓	✓	■	

Blood biochemistry test	◆	✓	✓	✓	✓	✓	✓	■	
Coagulation	◆	✓	✓	✓	✓	✓	✓	■	
Virological examination ¹	✓								
Pregnancy test (female subjects of childbearing age)	✓								
Electrocardiog- ram	◆	✓	✓	✓	✓	✓	✓	■	
Echocardiogra- phy	✓								
Imaging examination ²	✓	▲			✓			✓	
Radiation therapy		✓	✓	✓	✓	✓			
Combination medication ³	✓	✓	✓	✓	✓	✓	✓	✓	✓
Adverse event assessment ⁴	✓	✓	✓	✓	✓	✓	✓	✓	✓
Survival follow-up ⁵		✓	✓	✓	✓	✓	✓	✓	✓

◆ The examination results within 1 week can be used without repeating the measurement.

▲ The test results within 2 weeks before medication can be used without repeated measurements.

■ If there are any anomalies that have not been resolved before, evaluation will be conducted as needed

1. First, screen for HIV antibodies, five hepatitis B tests, hepatitis C antibodies, and human papillomavirus

(HPV) tests. When the test results indicate the possibility of active hepatitis B or C infection, further HBV DNA quantitative testing and HCV RNA quantitative testing are required to confirm the diagnosis;

2. The imaging assessment can be performed by esophageal angiography and chest and abdominal enhanced CT examination according to the doctor's choice (imaging examinations of the same part at different times should use the same detection technology as the baseline period). The evaluation sites are mainly the esophagus and mediastinal lymphatic drainage area, and other parts are evaluated as needed. After the screening evaluation, imaging evaluation is performed every 21 days during radiotherapy, within 1 week and 4 weeks after the end of radiotherapy, and every 12 weeks thereafter until the disease progresses or the subject is intolerant or withdraws. The examination time window is ± 7 days;

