3. Record the name, dosage, start and end time of combined medications and treatments, as well as the reasons for combined medications and treatments;

4. Adverse events that have occurred will be followed until they disappear, improve or stabilize and the investigators believe that no further follow-up is required, including AEs that occur within 7 days after the screening period and SAEs that occur within 30 days after the end of radiotherapy;

5. Patients will be followed up for survival every 12 weeks after PD, and can receive telephone visits, including patient survival status and tumor treatment status. The specific cause of death will be recorded in detail when it involves the following factors (primary tumor recurrence, bleeding, perforation, new lesions; recurrence or new metastatic lymph nodes within and outside the region, etc.);

6. During the efficacy follow-up period, evaluation was only performed during the first two follow-up visits.

2. Introduction

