4.1.4 Efficacy follow-up period

- Definition: From the end date of radiotherapy (D29) to the PD date
- Frequency (except for special items): The first review is on the 28th day after completion (W9D5), and then every 12 weeks starting from W9D5 until disease progression, with a window period of ± 7 days.
- Content:
 - 1) Film degree exam;
 - 2) Observation and recording of adverse events (AEs occurring within 7 days after the end of radiotherapy and SAEs occurring within 30 days);
 - 3) Hematology, biochemistry, electrocardiogram (if there are previously unresolved abnormalities, blood samples and other laboratory evaluations are warranted);
 - 4) Combined treatment.

4.1.5 Survival follow-up period:

- Definition: From PD date to death/loss to follow-up
- Frequency: Once every 12 weeks, window period ± 7 days
- Content:

- 1.Understand and record the subject's survival status, cause of death and time (telephone follow-up is possible);
- 2.Combined treatment.

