7.1.3 Subject discontinuation/withdrawal from study

- 1)Patients may request to withdraw from the study at any time.
- 2)Researchers may ask subjects to terminate or withdraw from the study for the following reasons:
 - Pregnancy;
 - Poor compliance with study interventions;
 - If a clinical adverse event (AE), laboratory abnormality, or other medical condition occurs, continued participation in the study will not be in the best interest of the subject;
 - Disease progression requiring discontinuation of intervention;
 - The subject meets the exclusion criteria (new or previously undetected) and cannot continue to participate in the study;
 - Subjects are unable to receive regularly scheduled study interventions.
- 3)A subject to discontinue or withdraw from the study should be recorded in the case report form (CRF). Subjects who signed informed consent and underwent randomization but did not receive the study intervention can be replaced. Subjects who signed informed consent, underwent randomization, received the study intervention, and subsequently withdrew or were withdrawn/discontinued from the study cannot be replaced.

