8.1.2 Events ending in death

1)The event endpoint was the time of subject death;

2)If the subject's death is confirmed but the time of death is not clear, the last follow-up time of the subject is taken as the event endpoint;

3)For patients who had not died at the time of analysis, the time of the last follow-up was used as the event endpoint;

4)For patients lost to follow-up, the time of the last follow-up was used as the event endpoint;

5)For patients with only survival, the time of baseline examination will be used as the end point.

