2.4.4 Special tips for efficacy evaluation

When nodular lesions are included in the total target lesion assessment and nodules decrease in size to a “normal” size (<10 mm), they will still have a lesion size scan reported. To avoid overestimation based on increased nodule size, measurements will be recorded even if the nodule is normal. As mentioned previously, this means that a subject with a complete response will not have a score of 0 on the CRF.

If efficacy confirmation is required during the trial, repeated “unmeasurable” time

points will complicate the optimal assessment of efficacy. The analysis plan for the trial must state that these missing data/assessments can be accounted for when determining efficacy. For example, in most trials, a subject's response of PR-NE-PR can be considered to have efficacy confirmation.

When a subject experiences an overall deterioration in health that requires discontinuation of treatment, but there is no objective evidence, this should be reported as symptomatic progression. Every effort should be made to assess objective progression even after treatment has been discontinued. Symptomatic deterioration is not an assessment of objective response: it is a reason to discontinue treatment. The objective response of such subjects will be assessed by the target and non-target lesions as shown in Tables a to c.

Cases defined as early progression, early death and inevaluable are study specific and should be clearly described in each protocol (depending on the treatment interval and duration).

In some cases, it is difficult to distinguish localized disease from normal tissue. When the evaluation of complete response is based on such a definition, we recommend that a biopsy be performed before the evaluation of response to localized complete response. When some subjects have abnormal imaging results of localized disease that are thought to represent fibrosis or scarring, FDG-PET is used to confirm the response to complete response with a similar assessment criteria to biopsy. In such cases, the use of FDG-PET should be prospectively described in the protocol and supported by reports in the specialist medical literature for this setting. However, it must be recognized that the limitations of FDG-PET and biopsy, including their resolution and sensitivity, may lead to false-positive results in the evaluation of complete response.

**Table a Evaluation at each time point - Subjects with target lesions

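### Survival follow-up opens only at the PD date, so subjects who leave the study before documented PD have no scheduled survival contact; separately, 7.1.3 and 4.1.5 conflict on subjects who progress

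*Protocol*

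**What the plan says.** - **Survival phase.** Section 4.1.5 defines it as "Definition: From PD date to death/loss to follow-up", every 12 weeks. Note 5 to the schedule in 1.3 agrees: "Patients will be followed up for survival every 12 weeks after PD, and can receive telephone visits".
- **Before PD.** The schedule row "Survival follow-up ⁵" is ticked at every treatment visit, at the end-of-treatment visit and in the column from D29 to PD. The content list of 4.1.4 (efficacy follow-up) has no survival item. Schedule note 2 ends imaging at progression, intolerance or withdrawal.
- **Leaving the study.** Section 7.1.3 says "Researchers may ask subjects to terminate or withdraw from the study for the following reasons". The reasons include adverse events, poor compliance and inability to receive scheduled treatment, all of which can occur before PD, and also "Disease progression requiring discontinuation of intervention".
- **Protective text.** Section 7.1 says that stopping the intervention is not leaving the study. Section 7.1.2 asks early withdrawals to complete the necessary study steps, without naming survival contact. Section 7.2 requires contact attempts before a subject is declared lost.
- **Analysis.** Section 8.1.2: "For patients lost to follow-up, the time of the last follow-up was used as the event endpoint". Section 8.1.1 counts death before progression as a PFS event.

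**The concern.** OS, 1-year OS and 2-year OS are named secondary endpoints. They need only vital status, which a telephone call can supply. The protocol ties the start of those calls to one event, documented PD, which a subject who leaves early may never reach. Clinical decline without imaging evidence does not supply it: the RECIST appendix (12.2, item 2.4.4) says "this should be reported as symptomatic progression" and treats it as a reason for stopping treatment, not as an objective assessment.

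Such a subject is censored at the last follow-up. Kaplan-Meier then assumes the same later risk as in those still followed. In a population aged 75 and over, where some leave because of toxicity or decline, that assumption is open to doubt. A SAP cannot repair this afterwards, because vital status that was never collected cannot be recovered by analysis.

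**Working it through.** **1. Who falls in the gap**

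| Subject | Survival contact stated? |
|---|---|
| On study, before PD | Yes, ticked in the 1.3 schedule |
| Stops treatment, stays on study | Yes, later procedures continue (7.1) |
| Documented PD, stays on study | Yes, every 12 weeks (4.1.5) |
| Misses visits before PD | Tracing attempts only (7.2); no continuing schedule |
| Withdrawn under 7.1.3 before PD | None named; 7.1.2 is generic |
| Withdrawn under 7.1.3 for PD | 4.1.5 says yes; withdrawal from the study implies no |

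The fourth and fifth rows are the gap. The sixth is a separate conflict.

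**2. Inputs for the size**

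The protocol gives no planning figure for OS, so there is none to reproduce. Its dropout step does reproduce: 41/(1 − 0.20) = 51.25, rounded up to 52.

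- Median OS 17 months, from an earlier elderly series described in 2.2. It is not a planning value of this trial. Exponential survival is assumed, so λ = ln 2/17 = 0.0408 per month.
- Fraction of leavers q = 20%, the dropout allowance in 9.1. Treating all of it as early exit before PD is an assumption; q = 10% is also shown.
- Exit time uniform over months 0 to 6 (assumption).
- Death hazard after exit k times λ (assumption; range shown).

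**3. Formula**

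If the hazard changes only after exit and leavers are censored there, Kaplan-Meier estimates exp(−λt): 61.3% at 12 months, 37.6% at 24 months, median 17.0 months. For t of at least 6 months, true survival is

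S(t) = (1 − q)·exp(−λt) + q·exp(−kλt)·g, with g = [exp(a) − 1]/a and a = 6(k − 1)λ.

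Example, q = 0.20, k = 2, t = 12: a = 0.2446, g = 1.133, so S = 0.8 × 0.613 + 0.2 × 0.376 × 1.133 = 0.490 + 0.085 = 0.576. The overstatement is 61.3 − 57.6 = 3.7 points.

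**4. Results for 20% leavers**

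| k | True 1-year OS (estimate 61.3%) | True 2-year OS (estimate 37.6%) | True median, months (estimate 17.0) |
|---|---|---|---|
| 0.67 | 62.9% | 40.0% | 18.1 |
| 1 | 61.3% | 37.6% | 17.0 |
| 1.5 | 59.3% | 35.0% | 15.9 |
| 2 | 57.6% | 33.3% | 15.0 |
| 3 | 55.0% | 31.4% | 13.9 |

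For k from 1.5 to 3, 1-year OS is overstated by 2.0 to 6.3 points and 2-year OS by 2.6 to 6.2 points. With 10% leavers the ranges are 1.0 to 3.2 and 1.3 to 3.1 points. At k = 1 there is no bias. At k = 0.67 and 20% leavers, OS is understated by 1.6 points at 1 year and 2.5 at 2 years.

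**5. A second model**

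Here leavers carry the different hazard from the start and exit uniformly over months 1 to 6 (simulation, 400,000 subjects, 20% leavers). True against estimated 1-year OS is 58.6% against 60.4% (k = 1.5), 56.6% against 59.6% (k = 2) and 53.6% against 58.2% (k = 3). At 2 years it is 34.7% against 37.1%, 32.9% against 36.5% and 31.0% against 35.6%. The overstatement is about 2 to 5 points, with the same pattern.

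**The case against.** The strongest reply is that the protocol does follow survival before PD, and this is largely right. The schedule ticks survival status from D1, stopping treatment is not leaving the study, and 7.2 asks for up to three telephone calls and, if necessary, a registered letter before loss is declared. A reader might infer from 4.1.5 alone that nobody has survival contact before progression; the documents do not support that. What stands is narrower: tracing under 7.2 ends in dropping out, and no passage gives continuing survival contact to a subject who has left.

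A reader might also infer from 7.1.3 that progressors are generally removed from OS. The ground is permissive and concerns progression that requires stopping the intervention. Treatment lasts about five weeks (4.1.2) and the planning median PFS is 16 to 18.2 months (9.1), so on its wording it bears mainly on progression during treatment. The conflict with 4.1.5 is real but small, and distinct from the gap before PD.

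Finally, a reader might conclude that the deaths lost are those of the patients who do worst, so that reported OS will be too high. The protocol says nothing about the number or prognosis of leavers. Dropout in 9.3.1 covers any failure to complete follow-up, including loss after PD, so 20% early leavers before PD is a high figure. Even 6 points is within one standard error of a 1-year estimate from 50 subjects: √(0.613 × 0.387/50) = 6.9 points, ignoring censoring. OS is secondary and carries no hypothesis. These points limit the severity. They do not close the gap: imprecision does not cancel a systematic error, and this one can be avoided.

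**Conclusion.** The point holds as a gap in data collection. After exit from the study before documented PD, no survival contact is stated beyond the 7.2 attempts, and OS is cut at last follow-up. Sections 7.1.3 and 4.1.5 also conflict for subjects who progress and must be reconciled.

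The size is conditional: about 2 to 6 points at 1 and 2 years if 20% leave in the first six months and their hazard is 1.5 to 3 times higher, and roughly half that at 10%. The direction depends on the leavers' hazard, which the documents do not give. Beyond OS, a death after exit and before progression is a PFS event under 8.1.1. If it goes unseen, the subject is censored at the last tumour assessment, so the primary endpoint can be affected too. This is a worthwhile, inexpensive correction; it does not show that the trial's OS will be wrong.

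**What to change.** - In 4.1.5 and schedule note 5, start 12-weekly survival contact at PD, or when study visits stop for any reason without PD, by telephone as already allowed, for every treated subject unless consent to contact is withdrawn.
- Add survival status to the content list of 4.1.4, to match the schedule.
- Reconcile 7.1.3 with 4.1.5 so that progression leads into survival follow-up and not out of the study.

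The cost is a short amendment and telephone calls every 12 weeks for perhaps 5 to 10 subjects (10% to 20% of the 50 planned in the summary). Reported OS may be slightly lower than it would otherwise have been.

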4.2 Dose selection

Nimotuzumab injection is a colorless clear liquid, administered by intravenous infusion, and the administration process should last for more than 60 minutes. The BPL-IST-ESO-057 study used a 400 mg weekly dosing regimen for nimotuzumab. Considering the decreased tolerance of elderly patients, this study used a 400 mg dose for the first administration, and a 200 mg dose for subsequent treatment courses due to the poor tolerance of elderly patients.

4.3 Definition of end of study

The study is considered to be completed when the subject no longer needs to be examined or the last visit of the last subject is completed.

5. Study population

5.1 Inclusion criteria

Patients must meet all of the following criteria to be eligible for this trial:

- 1)The patients voluntarily participated in this study, signed the informed consent, had good compliance, and cooperated with the follow-up;
- 2)Age 75 and above, regardless of gender;
- 3)ECOG score 0-1;
- 4)Esophageal cancer confirmed by histology or cytology;
- 5)According to RECIST 1.1 (see 12.2. Response Evaluation Criteria for Solid Tumors Version 1.1 for details), there is at least one measurable lesion, and the measurable lesion should not have received local treatment such as radiotherapy (lesions located in the previous radiotherapy area can also be

selected as target lesions if they are confirmed to have progressed and meet the RECIST 1.1 criteria);

6)Patients with stage II-IVB according to AJCC (8th edition, 2018) (IVB included metastasis to the celiac trunk or supraclavicular lymph nodes only) who are not suitable for or refuse surgery can tolerate concurrent chemoradiotherapy and targeted therapy;

7)Expected survival time \geq 12 weeks;

8)The major organs function normally, that is, they meet the following criteria:

●Blood test:

- a.HBG \geq 90 g/L;
- b.ANC \geq 1.5×10^9 /L;
- c.PLT \geq 80×10^9 /L;

●Biochemical tests:

- a.ALB \geq 30 g/L;
- b.ALT and AST \leq 2.5 ULN; if there is liver metastasis, ALT and AST \leq 5 ULN;
- c.TBIL \leq 1.5ULN;
- d.Plasma Cr \leq 1.5ULN or creatinine clearance (CCr) \geq 60ml/min;

9)Echocardiographic assessment: left ventricular ejection fraction (LVEF) \geq lower limit of normal value (50%);

10)Female of childbearing age must agree to use contraceptive measures (such as intrauterine devices, birth control pills or condoms) during the study and within 6 months after the end of the study; the serum or urine pregnancy test is negative within 7 days before study enrollment, and they must be non-breastfeeding patients; men must agree to use contraceptive measures during the study and within 6 months after the end of the study.

5.2 Exclusion criteria

Patients who meet any of the following criteria will be excluded from this trial:

- 1)Received EGFR monoclonal antibody or EGFR-TKI within six months;
- 2)Participated in other interventional clinical trials within 30 days before screening;
- 3)Patients with serious concurrent diseases, such as heart failure, high-risk uncontrollable arrhythmias, severe myocardial infarction, refractory hypertension, renal failure (CKD-4 and above), thyroid dysfunction, mental illness, diabetes, severe chronic diarrhea (more than 7 bowel movements per day), or patients who are considered unsuitable to participate in this clinical study by the researchers;
- 4)Patients with brain metastases with symptoms or symptom control time of less than 3 months;
- 5)Having a history of other malignant tumors (except for cured cervical carcinoma in situ or basal cell carcinoma of the skin and other malignant tumors that have been cured for more than 5 years);
- 6)The presence of active infection or active infectious disease;
- 7)Patients with multi-segment esophageal malignant tumors or signs of esophageal fistula or perforation;
- 8)Patients whose tumors have invaded important blood vessels as shown by imaging or who are judged by the researchers to be very likely to invade important blood vessels and cause fatal hemorrhage during the follow-up study;
- 9)Those who are allergic to the drugs or their ingredients used in this program;
- 10)Peripheral neuropathy or hearing loss of grade 2 or higher according to the criteria of Common Terminology for Adverse Events (NCI CTCAE V5.0);
- 11)Pregnant or breastfeeding women;

- 12)Patients with a history of psychotropic drug abuse and unable to quit or patients with mental disorders;
- 13)Those who are considered unsuitable to participate in this study by the researcher;
- 14)Those who are unwilling to participate in this study or unable to sign the informed consent.

5.3 Screening failure

Screening failure is defined as a subject who consents to participate in a clinical trial but is not randomized to receive the study intervention or enrolled in the study. Information on screening failure should include demographics, details of screening failure (eligibility criteria, and any serious adverse events).

Patients who do not meet the criteria for participating in the trial (screening failure) can undergo rescreening. The screening number of the subject in the rescreening is the same as the screening number of the initial screening.

6. Study intervention

6.1 Study intervention management

6.1.1 Description of study intervention

Intervention Name	Dosage form	Manufacturer	Specification	Administration route	Storage and stability
Nimotuzumab	Injection	Biotech Pharmaceutical Co., Ltd.	50mg/bottle (10ml)	Intravenous injection	This product should be stored and transported at 2°C-8°C and should not be frozen. The shelf life is 24 months. After dilution with normal

					saline, this product can remain stable for 12 hours at 2°C-8°C and 8 hours at room temperature. If stored for longer than the above time after dilution, it should not be used.
S-1	Capsule	Jiangsu Hengrui Medicine Co., Ltd./Qilu Pharmaceutical Co., Ltd.	20mg/capsule	Oral	Protect from light, seal tightly, and store at room temperature.

6.1.2 Dosage and administration

S-1: 40-60 mg/m², po, D1, BID, 5 weeks;

Nimotuzumab 400 mg, iv, D1, week 1;

Nimotuzumab 200 mg, iv, D8, QW, Week 2-Week 5.

Radiation Therapy:

Intensity modulated radiation therapy (IMRT) technology is used to irradiate the involved field. The patient is placed in a supine position and fixed with the head, neck, shoulder or body membrane. The patient is simulated and positioned under CT. The CT image is transmitted to the treatment planning system. Combined with esophageal barium meal contrast, gastroscopy or ultrasound gastroscopy or PET-CT images, the esophageal tumor target volume (GTV) is outlined layer by layer on the enhanced CT image; the clinical target volume (CTV) is the GTV with an axial expansion of 0.6 to

0.8 cm and an upper and lower expansion of 2.0 to 3.0 cm; the planned target volume (PTV) is the CTV with an expansion of 0.5 to 0.8 cm. The metastatic lymph nodes are outlined as GTV-nd, and the GTV-nd with an expansion of 0.8 to 1.0 cm is PTV-nd. The prescription dose requires that 95% of PTV and PTV-nd receive 50 Gy /25 F , with a single dose range of 2.0 Gy/F. The target dose distribution and the dose of organs at risk are evaluated layer by layer on the cross section, and the dose-volume histogram (DVH) is combined to evaluate and optimize the treatment plan. The maximum spinal cord dose is <45 Gy, lung V20 <28%, V30 <20%, and the average lung dose Dmean \leq 15 Gy. After the treatment plan is confirmed, the dose is verified on the treatment machine, and the treatment plan is executed after it is accurate.

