Study intervention	
1.Radiation Therapy
 
The prescription dose required that 95% PTV and PTV-nd receive 50-60 Gy /25-30 F , with a single dose range of 2.0 Gy/F, 5 days a week, external beam radiation to the chest .
 
2.Treatment
 
S-1: 40-60 mg/m² , po, D1, BID, 5 weeks;
 
Nimotuzumab 400 mg, iv, D1, week 1;
 
Nimotuzumab 200 mg, iv, D8, QW, Week 2-5.

Study duration	The estimated time from the start of the study to the completion of data analysis is 40 months
Visit duration	The planned enrollment period for this study is 12 months, and the time required for each subject to complete all visits are 24 months.

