4.1.2 Treatment period

●Definition: First radiotherapy day W1D1 - last radiotherapy day W5D5

●Window period: treatment ± 2 days, imaging ± 7 days, pre-dose items -1 day.

●Content:

1)Before WxD1 administration

a.Body surface area (BSA);

b.Physical examination

c.Vital signs;

d.ECOG performance status score;

e.Blood samples and other laboratory evaluations (hematology and clinical chemistry);

f.Electrocardiogram (12 leads);

2)Administer nimotuzumab (see 6.1.2. Dosage and administration);

3)Administer Tegafur (see 6.1.2. Dosage and Administration);

4)Administer radiation therapy (see 6.1.2. Dosage and administration);

5)Observe and record adverse events;

6)Combined treatment;

7)Imaging examination: Review every 21 days after W1D1 (such as W1D22).

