4.1.3 End of treatment visit

●Definition: visit at the end date of radiotherapy

●Window period: ± 3 days

●Content:

1) Physical examination and vital signs check (at the end of radiotherapy);

- 2) ECOG performance status;
- 3) QoL (assessed at the first two efficacy follow-ups);
- 4) Nutritional status;
- 5) Hematology and clinical biochemistry (at the end of radiotherapy);
- 6) 12-lead electrocardiogram (at the end of radiotherapy);
- 7) Observation and recording of adverse events (AEs occurring within 7 days after the end of radiotherapy and SAEs occurring within 30 days);
- 8) Blood samples and other laboratory evaluations (hematology and clinical chemistry) are required if there are previously unresolved abnormalities;
- 9) Combined treatment.

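### The synopsis allows 50-60 Gy in 25-30 fractions, but section 6.1.2 prescribes 50 Gy in 25 fractions and the W1D1-W5D5 radiotherapy period has room for no more than 25

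*Protocol*

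**What the plan says.** - **Protocol 1.1 (Summary, study intervention):** "The prescription dose required that 95% PTV and PTV-nd receive 50-60 Gy /25-30 F", at 2.0 Gy per fraction, five days a week.
- **Protocol 6.1.2:** "The prescription dose requires that 95% of PTV and PTV-nd receive 50 Gy /25 F", again at 2.0 Gy per fraction. It gives no range and no option to go higher.
- **Protocol 4.1.2:** refers to 6.1.2 for giving radiotherapy and defines the treatment period as "First radiotherapy day W1D1 - last radiotherapy day W5D5", with the windows "treatment ± 2 days, imaging ± 7 days".
- **Drugs:** sections 1.1 and 6.1.2 agree. S-1 runs for five weeks, and nimotuzumab ends in week 5 ("Nimotuzumab 200 mg, iv, D8, QW, Week 2-Week 5").
- **Protocol 4.1.3 and 4.1.4:** the end-of-treatment visit is defined as the "visit at the end date of radiotherapy". The first efficacy review is 28 days after completion and is labelled W9D5.

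**The concern.** Both sections state the prescription dose to the same target volumes at the same dose per fraction, but they permit different totals. A synopsis may be shorter than the body. Here it authorises doses that the body does not, and for any dose above 50 Gy the two sections cannot both be followed.

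Radiation is a core part of the regimen under test, and section 5.1 restricts entry to patients aged 75 and over. Section 4.2 gives poor tolerance in the elderly as the reason for lowering the nimotuzumab dose, so a total radiation dose left open by 20% matters for safety. The higher dose is also one a clinician might plausibly choose: the background in section 2.2 cites a nimotuzumab chemoradiotherapy study with a median dose of 60 Gy. Someone prescribing from the synopsis could choose it in good faith and then be recorded as deviating from 6.1.2.

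**Working it through.** **Inputs.** 2.0 Gy per fraction (1.1 and 6.1.2); five fractions a week (1.1); 25 fractions (6.1.2) against 25-30 (1.1); radiotherapy from W1D1 to W5D5 with a ±2-day treatment window (4.1.2); first review 28 days after completion at W9D5 (4.1.4).

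**Each prescription is consistent within itself.**
- 25 × 2.0 Gy = 50 Gy; 25 / 5 = 5 weeks.
- 30 × 2.0 Gy = 60 Gy; 30 / 5 = 6 weeks.

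**Length of the treatment period.**
- W5D5 = 4 × 7 + 5 = day 33. With the window, 33 + 2 = day 35.
- Cross-check from 4.1.4: W9D5 = 8 × 7 + 5 = day 61, and 61 − 28 = day 33. This again puts completion at W5D5.

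**Fractions that fit, counting weekdays.**

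| Start weekday | By day 33 | By day 35 | Fraction 26 on | Fraction 30 on |
|---|---|---|---|---|
| Monday | 25 | 25 | day 36 | day 40 |
| Tuesday | 24 | 25 | day 36 | day 42 |
| Wednesday to Friday | 23 | 25 | day 36 | day 42 |

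The limit by day 35 is 25 × 2.0 = 50 Gy for every start weekday. The ±3 days in 4.1.3 is a window for the visit, not for treatment. Even if it were borrowed (day 36), it would admit only 26 fractions, or 52 Gy.

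**Size of the conflict at the top of the synopsis range.**
- Dose: 60 − 50 = 10 Gy; 10 / 50 = 20% above 6.1.2.
- Fractions: 30 − 25 = 5, which is one extra week.
- Timing: 40 − 33 = 7 days past W5D5, and 40 − 35 = 5 days past its window.
- Drug cover, reading S-1 as days 1-35 with the last nimotuzumab dose on day 29: fractions 26-30 deliver 5 × 2 = 10 Gy after the drug weeks; 10 / 60 = 17% of the total.

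In steps of one fraction the synopsis range contains 50, 52, 54, 56, 58 and 60 Gy. Only 50 Gy agrees with 6.1.2 and 4.1.2.

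**The case against.** **The documents do not say which line was intended.** This stands. That the synopsis is the faulty line is an inference. It is well supported: 4.1.2 points to 6.1.2, W5D5 holds 25 fractions, W9D5 implies completion on day 33, the drugs stop at five weeks, and the schedule in 1.3 has no treatment column after D29.

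**Day labels in this protocol are loose.** Section 4.1.4 also dates the end of radiotherapy at D29 ("From the end date of radiotherapy (D29) to the PD date"), as does the end-of-treatment column in 1.3. By day 29 only 4 × 5 + 1 = 21 fractions (42 Gy) fit, so that label taken literally would exclude 50 Gy as well. It is best read as a clerical slip, because 4.1.3 ties the visit to the actual end of radiotherapy; no weight is put on it here. W5D5 has separate support from the W9D5 review. The conflict between 1.1 and 6.1.2 does not depend on any day label.

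**Follow-up would be little disturbed by a sixth week.** This is correct. After 60 Gy the 28-day review would fall on day 40 + 28 = 68, inside the ±7-day window around day 61.

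**Exposure is limited.** A patient given 50 Gy in 25 fractions satisfies both texts, and staff are sent to 6.1.2. No effect on the sample size or the PFS analysis is shown. This also stands. The case rests on an unclear treatment dose, not on a numerical effect on the results.

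**Conclusion.** The contradiction is real and should be corrected. The synopsis permits up to 10 Gy (20%), 5 fractions and one week more than 6.1.2 prescribes and 4.1.2 accommodates. Neither the start weekday nor the treatment window removes the difference.

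Three readings are used. The 2-day window is taken to apply to the end of radiotherapy, which is the generous reading; without it the limit is tighter still. Radiotherapy is taken to be given on weekdays. S-1 is taken to run on days 1-35, which affects only the statement about drug cover. That the synopsis is the line to change is a strong inference, and the sponsor should confirm the intended dose.

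**What to change.** If 50 Gy is intended, change the synopsis in 1.1 to 50 Gy in 25 fractions, matching 6.1.2. This is one line, with no added visits or patients.

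If up to 60 Gy in 30 fractions is intended for some patients, amend 6.1.2 and the W5D5 end of the treatment period in 4.1.2. State who receives more than 50 Gy and whether S-1 and nimotuzumab continue into week 6. This is a larger change, because it redefines the regimen.

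As a clerical tidy-up in the same revision, replace D29 as the end of treatment or radiotherapy in 1.3 and 4.1.4 with the actual date of the last fraction (W5D5, day 33, for 25 fractions from a Monday start).
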